#### 1. Abstract

Patient preference for medications in place of osmotic dilators as cervical preparation is well known. Twenty-four to 48 hours following mifepristone, vaginal and buccal misoprostol have demonstrated equal efficacy in second-trimester medical abortion but have not been compared as cervical preparation for second-trimester surgical abortion.

This study will randomize participants undergoing a second-trimester surgical abortion between 16 0/7-20 6/7 weeks gestation to 200mg mifepristone followed 20-24 hours later with 400mcg vaginal misoprostol and buccal placebo versus 400mcg buccal misoprostol and vaginal placebo 1-2 hours prior to the procedure. Primary outcome is intraoperative procedure time as measured by time of first instrument in the uterus (dilator if further dilation is required or forceps if no further dilation required) to last instrument out of the uterus. The study uses a superiority design and is powered to detect a 4-minute difference in procedure time from a baseline of  $10 \pm 5$  minutes with 90% power and two-tailed alpha of 0.05 requiring 33 participants in each arm. To account for 10% dropout or disgualification, 72 participants will be recruited. Secondary outcomes include cervical dilation assessed with largest Pratt dilator initially accepted without resistance, patient report of pain (as measured on an 11-point VAS scale), side effects, acceptability, and recommendation to friends (as measured on a 5-point Likert scale), and provider estimation of blood loss, complications, ease of dilation (as measured on an 11-point VAS scale), acceptability, and recommendation to other patients (as measured on a 5-point Likert scale).

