### 5.6 Criteria for discontinuation

Any participants who meet any one of the following criteria at any point after enrollment will be discontinued from the study:

- Urgent need for a D&E
- Decision not to proceed with the D&E
- Decision to stop participation in the study

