### 5.9 Data analysis

STATA statistical software (StataCorp LP, College Station, TX, www.stata.com) will be used to analyze the baseline characteristics of the populations based on the study questionnaires completed by participants prior to their procedure. Primary and secondary outcomes will be recorded as described above in 5.4. Both primary and secondary outcomes will be analyzed using t-tests or appropriate non-parametric comparison tests as appropriate. The perception assessments (VAS) will be assessed using non-parametric analysis. The primary analysis will be based on intention to treat.

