### 5.10 Number of subjects and statistical power

Sample size is based on prior studies assuming that longer procedure times reflect a need for further dilation and manipulation. Procedure time is defined in this study as first instrument passing into the uterus until last instrument out of the uterus. Previous studies have defined a 3-minute for 14-16 week gestations or 5-minute change for 19-24 week gestations as clinically significant. For this study evaluating 16 - 20 6/7 week gestations, we chose 4-minute difference as clinically significant. Using a superiority design, in order to detect a 4-minute change in procedure time from a baseline of 10 minutes with a standard deviation (SD) 5 minutes), with a two-tailed alpha of 0.05 and power of 90%, 33 women will be needed in each arm. We plan to recruit 72 participants due to post-enrollment exclusion.

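### Do 72 recruits fall short of the stated 10% loss allowance, and 33 per arm short of 90% power?

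*Combined protocol and SAP*

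**What the plan says.** The abstract and section 5.10 give the same calculation. The primary outcome is procedure time. On the target difference, section 5.10 says "we chose 4-minute difference as clinically significant". The baseline is 10 minutes with an SD of 5, and the conclusion is "with a two-tailed alpha of 0.05 and power of 90%, 33 women will be needed in each arm". The abstract words the result as "with 90% power and two-tailed alpha of 0.05 requiring 33 participants in each arm".

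Both places raise the total to 72, but for differently worded reasons. The abstract gives a rate: "To account for 10% dropout or disgualification, 72 participants will be recruited". Section 5.10 gives none: "We plan to recruit 72 participants due to post-enrollment exclusion". Section 5 divides the 72 into 36 per arm.

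For the analysis, section 5.9 allows "t-tests or appropriate non-parametric comparison tests" and adds: "The primary analysis will be based on intention to treat". Among the grounds for discontinuation in section 5.6 is "Decision not to proceed with the D&E", which would leave a woman with no procedure time.

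**The concern.** Two figures look slightly too favourable.

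The first is the loss allowance. Dropout is normally a share of those recruited. A tenth of 72 is 7.2, and 72 less 7.2 is below the 66 that the plan says it needs. Section 5.10 does not repair this, because it states no rate. Someone tracking attrition against the abstract could think a seventh loss is covered, when it takes the trial to 65.

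The second is the power. The figure of 33 per arm comes from a formula that treats the SD as known. A two-sample t-test, one of the analyses section 5.9 allows, estimates the SD and needs slightly more women for the same power.

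At stake would be a trial with less power than it advertises for the difference it calls clinically significant.

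**Working it through.** **Inputs.** From section 5.10 and the abstract: difference 4 minutes, SD 5 minutes, two-sided alpha 0.05, power 90%, 33 per arm, 72 recruited. From section 5: 36 per arm. From the abstract alone: 10% loss.

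**Step 1. Reproduce the plan's 33 per arm.** By the normal approximation,

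n per arm = 2 × (1.960 + 1.2816)² × 5² / 4² = 32.84, rounded up to 33.

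Power at n₁ and n₂ is Φ(4 / (5 × √(1/n₁ + 1/n₂)) − 1.960). At 33 and 33 this is Φ(3.250 − 1.960) = Φ(1.290) = 90.1%. The plan's figure is reproduced.

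**Step 2. Check the loss allowance.**

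- Required: 2 × 33 = 66.
- Left after 10% of 72 is lost: 72 × 0.9 = 64.8, about 65.
- Margin in 72: 72 − 66 = 6 women, which is 6/72 = 8.3% of recruits or 6/66 = 9.1% of the required number.
- Recruits needed to keep 66 after a 10% loss: 66/0.9 = 73.3, so 74 with equal arms.
- Adding 10% to the required number instead: 66 × 1.1 = 72.6. Rounding that down gives 72, which may be how the figure arose; the documents do not say.

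The stated 10% is therefore not quite met. The gap from the strict figure is 74 − 72 = 2 women.

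**Step 3. What that gap does to power.** The normal approximation uses the formula in step 1. The t-test column uses the noncentral t distribution with the same difference and SD.

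| Women analysed per arm | Normal approximation | Two-sample t-test |
|---|---|---|
| 36 and 36 (all 72) | 92.4% | 91.7% |
| 33 and 33 (6 lost, 3 per arm) | 90.1% | 89.3% |
| 32 and 33 (10% lost) | 89.7% | 88.8% |

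For the last row by the normal approximation: √(1/32 + 1/33) = 0.2481; 4/(5 × 0.2481) = 3.2245; Φ(3.2245 − 1.960) = Φ(1.265) = 89.7%.

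Uneven losses matter little. If all six came from one arm (30 and 36), √(1/30 + 1/36) = 0.2472 and the normal-approximation power is Φ(3.236 − 1.960) = Φ(1.276) = 89.9%.

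**Step 4. The t-test requirement.** Exact 90% power needs 33.83, so 34 per arm (90.2%). That is one woman per arm more than planned for analysis, and fewer than the 36 per arm enrolled.

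**Step 5. Compare with the other uncertainty in the calculation.** At 32 and 33 the t-test detects 4.08 minutes with 90% power, against the planned 4. The difference of 0.08 minutes is about 5 seconds. At the same numbers, t-test power is 90.0% if the SD is 4.9 and 85.6% if it is 5.25. A 5% error in the assumed SD (5.25/5 = 1.05) costs 88.8 − 85.6 = 3.2 points, several times the 90.1 − 89.7 = 0.4 points at issue in the loss allowance.

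**The case for a change.** The strongest argument for acting is that the abstract is the only place that states a loss rate, that the rate is wrong as written, and that a correction would be short and need no extra women. A likely origin in 66 × 1.1 explains the slip without making it right, since even that method would round up to 73. The power statement can also be called optimistic, because a t-test is among the planned analyses and has 89.3% power at 33 per arm.

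The loss arithmetic stands in full: 72 does not keep 66 women after a 10% loss, and nothing elsewhere in the plan says that it does.

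The power argument does not stand as an error. The plan names no sample-size formula, never describes its 90% as an exact t-test figure, and leaves the choice between a t-test and a non-parametric test open. The normal approximation is a conventional basis for planning, and the 0.7-point shortfall from 90% reflects only which formula is used.

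Nor is the reader left unable to see the margin. The required 33 per arm and the total of 72 stand together in both places, so the spare six women follow by subtraction. Under intention to treat, a woman disqualified after enrolment but with a recorded time stays in the analysis. Only women without a procedure time reduce the sample, and the plan gives no separate estimate of how many there will be.

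**Conclusion.** No change to the plan is needed. The 10% in the abstract is a rounding slip: the true allowance is 6 women, 8.3% of recruits, and strict cover for 10% would take 2 more women. By the plan's own method, a full 10% loss gives 89.7% power instead of 90.1%, and both round to the stated 90%. The calculation of 33 per arm is correct as a normal approximation. By an exact t-test the corresponding figures are 88.8% and 89.3%, at most 1.2 points below 90%.

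Stating the allowance as 8.3% would leave the enrolment target, the analysis, the result and its interpretation as they are. If the abstract is edited for other reasons, the percentage can be tidied as a matter of copy-editing.

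This rests on the plan's 4-minute difference and 5-minute SD, on a comparison of means, and on no more than about 10% of women lacking a procedure time. Heavier loss or a larger SD would lower power, but that would be a separate matter from this slip.

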## 2. Specific Aims

This study aims to compare mifepristone and buccal misoprostol to mifepristone and vaginal misoprostol for cervical preparation for second trimester D&E. We hypothesize that giving oral mifepristone 20-24 hours and vaginal misoprostol 1-2 hours prior to D&E will provide better cervical dilation than mifepristone 20-24 hours and buccal misoprostol 1-2 hours prior to D&E. The primary outcome of the study will be length of procedure as measured by first instrument in the uterus (dilator if further dilation is required or forceps if no further dilation required) to last instrument out of the uterus. Secondary outcomes will include cervical dilation achieved as measured by the largest size Pratt dilator accepted without resistance prior to the start of the procedure, total dilation required, blood loss, pain, complications, provider assessment of difficulty, and provider and patient acceptance and recommendation for other patients.

## 3. Previous research

The addition of mifepristone, a progesterone antagonist, to a misoprostol regimen has been shown to significantly decrease the medication-to-abortion interval in second-trimester induction terminations. Vaginal administration has demonstrated improved dilation as compared to buccal administration but it is known that patients prefer buccal administration. A comparison of mifepristone and vaginal versus mifepristone and buccal misoprostol has not been studied prior to second-trimester surgical abortion.

A Cochrane review (2010) of cervical preparation for second-trimester D&E did not recommend mifepristone and misoprostol for cervical priming due to high rates of preprocedural expulsions.  However, the primary basis for this conclusion is the trial by Carbonell et al. in which the 48-hour interval between the medications accounts for the high out-of-facility expulsion risk. A retrospective cohort of over 200 women between 14 and 19 6/7 weeks gestation showed no difference in difficulty of cervical dilation for patients receiving mifepristone 24–48 hours misoprostol as compared to osmotic dilators prior to surgical abortion. Two out of facility expulsions occurred in the mifepristone-misoprostol arms but the timing of medication to expulsion interval is not reported.

More recent studies have limited the timing of mifepristone to 24 hours or less prior to procedure. Mifepristone only has been shown to provide adequate cervical dilation as compared to osmotic dilators to 16 weeks gestation with noninferiority design to detect a 3-minute difference in procedure time. A 24-hour interval between 200mg mifepristone and 400mcg buccal misoprostol has been shown as non-inferior to osmotic dilators for total procedure time for 15-18 week surgical abortions. Mifepristone and one-set of osmotic dilators was found to be non-inferior for total procedure time as compared to two sets of osmotic dilators for surgical abortion 19-23 6/7 weeks gestation.

The addition of mifepristone has benefit as a cervical priming agent as an adjunct or alternative to osmotic dilators for surgical abortion, but it is not known whether the addition of vaginal versus buccal misoprostol changes cervical dilation and thus procedure time outcomes.

# 4. Rationale

Second-trimester dilation and evacuation (D&E) procedures at 14 weeks or greater require cervical preparation.  Osmotic dilators have traditionally been used for cervical dilation but it is known that patients prefer medication to dilators. Misoprostol alone can be used for early second trimester dilation but is associated with increased requirement for dilation. Adding mifepristone to buccal misoprostol was found to be non-inferior to osmotic dilators for procedure time for 15-18 weeks gestation. Mifepristone alone was found to provide adequate cervical preparation up to 16 weeks gestation. Vaginal misoprostol is associated with fewer gastrointestinal side effects as compared to buccal administration and is associated with a shorter induction to delivery interval. This study aims to evaluate mifepristone and buccal versus mifepristone and vaginal misoprostol (with an interval of at least 20 hours between the medications) for gestational ages 16 0/7 to 20 6/7. This study will contribute to the literature evaluating medication only cervical preparation prior to second-trimester procedures.

### 5. Research design and General Methodological Approach

We have chosen a randomized controlled trial to ensure that neither patient nor provider will be biased by medication choice. Seventy-two English or Spanish-speaking women greater than 18 years of age and at 16 0/7-20 6/7 weeks gestation will be enrolled with 36 women in each arm.

Computer-generated randomization will be utilized to assign treatment arms and the vaginal misoprostol and buccal placebo and buccal misoprostol and vaginal misoprostol will be prepared according to randomization scheme by the research pharmacy in opaque-sealed envelopes as to blind participants and providers.

One arm will receive mifepristone 200mg orally 20–24 hours prior and misoprostol 400mcg (two 200mcg tablets) vaginally 1–2 hours prior and placebo (two lactose tablets designed to appear similar to misoprostol) buccally 1–2 hours prior to D&E. The second arm will receive mifepristone 200mg orally 20–24 hours prior and misoprostol 400mcg (two 200mcg tablets) buccally and placebo (two lactose tablets designed to appear similar to misoprostol) vaginally 1–2 hours prior to surgical abortion. The patients will place the tablets in the pre-operative area from pre-marked envelopes. The patient will be instructed to take the medication in the envelope marked buccally (misoprostol 400 mcg or placebo) to be placed in the cheek pouch for 30 minutes and then remaining swallowed and the envelope marked vaginally (misoprostol 400mcg or placebo) to be placed vaginally as far as the patient can insert with her finger. The patient will be witnessed taking the buccal medication but the patient will be given privacy for vaginal administration. The time will be recorded in the patient's chart. Prior to the procedure, patient assessment of medications will be obtained as detailed in 5.5.

At 1–2 hours after misoprostol and placebo administration, the participant will be brought into a procedure room for a dilation and evacuation (D&E). Prior to the D&E, an assessment of cervical dilation will be made as assessed by largest size Pratt dilator accepted without resistance starting with 39–French. Only the attending will assess cervical dilation but procedures will be performed by the attending and residents-in-training. Type of provider will be recorded.

Five time estimates will be recorded: 1) time interval between mifepristone and misoprostol/placebo placement, 2) time interval between misoprostol insertion and assessment of cervical dilation 3) total procedure time (speculum in to speculum out), 4) intraoperative procedure time designated as start of additional dilation (if required) or start of uterine instrumentation (if further dilation not required) to time of last instrument removed from uterus. Following the procedure, provider assessment will be obtained as detailed in section 5.5.

## 5.1 Criteria for selection of subjects

The trial will be conducted at Virginia Commonwealth University Medical Center (VCUHS) and Virginia League of Planned Parenthood (VLPP) over the course of approximately fourteen months. The study will enroll healthy women, over 18 years of age, eligible for non-urgent D&E at 16 0/7 weeks to 20 6/7 weeks gestation, confirmed by sonogram. Patients presenting to either office in consultation for a D&E will be recruited for participation. Exclusion criteria will include: emergent need for D&E, intrauterine infection, fetal demise, molar pregnancy, multiple pregnancy, uterine anomaly or significant distortion of the uterus with fibroids, intolerance, allergy or contraindication to mifepristone or misoprostol.

## 5.2 Subject recruitment and allocation

Both VCUHS and VLPP serve representative samples of Richmond, Virginia. Second trimester services at VLPP started in 03/2014.

After the patient has completed the counseling process and decided to proceed with an induced abortion, she will be approached by either a co-investigator or research staff member and asked to participate in the study. A detailed explanation of the study will be provided and informed consent obtained in English or Spanish, according to patient preference. A copy of the informed consent will be given to the patient. Eligibility for the study will be confirmed.

The VCU Investigational Research pharmacy will prepare the allocation sequence for preparation of allocation envelopes. Subjects will be allocated in blocks of 4–6. A researcher not involved in subject recruitment and without participant contact will prepare sequentially numbered opaque envelopes with the assigned, blinded pills for vaginal or buccal administration (misoprostol or placebo) enclosed. The envelope will not contain information that would reveal the group assignment. The envelope will not be assigned to a participant until eligibility is confirmed. The envelope will not be opened until just prior buccal and vaginal placement. The allocation number will be recorded twice in the participant's chart. The envelope will be attached to the chart. The envelope will only have the allocation number on the outside and the blinded pills inside.

# 5.3 Description of the drugs and devices to be studied

Mifepristone is a progesterone receptor antagonist. The brand name Mifeprex is manufactured for Danco Laboratories, LLC with address: [name]. The dose of mifepristone to be utilized in this study is 200 mg.

Misoprostol is a synthetic prostaglandin E1 analogue. Generic misoprostol is manufactured by Taj Pharmaceuticals Ltd. with address as follows: [name] (US FDA approved manufacturer). Brand name misoprostol, Cytotec, is manufactured by Pfizer, Inc. with address: [name]. The dose of misoprostol to be utilized in this study is 400 mcg.

Both misoprostol and placebo pills will either be encapsulated or will be supplied in a troche. This is to be determined. They will be created by the VCU investigational research pharmacy: VCU research pharmacy: [name]

### 5.4 Admission procedure

Recruitment will begin July 2015 and extend for approximately fourteen-months, ending once enrollment is complete. Patients presenting to VCUHS or VLPP will be enrolled, as described in 5.2. Following enrollment, the patient will complete an admission form including baseline demographics and reproductive history.

After ensuring the patient meets eligibility criteria, has signed consents and following the preoperative assessment, a research staff member will give the patient mifepristone 200mg to take orally in the staff member's presence and the time will be recorded in the patient's chart. The following day, a research assistant will dispense two numbered (one vaginal and one buccal) envelopes as described in 5.2 upon arrival to VCU Medical Center for the procedure. Prior to dispensing the envelope, the research staff member will examine the allocation numbers as recorded in the patient's chart to ensure a match.

### 5.5\_Patient and Provider Assessment

The patient will complete the survey immediately prior to the procedure to provide an accurate assessment of medication acceptability and side effects prior to anesthesia. The patient survey will assess pain (as measured using an 11-point visual analog scale) and acceptability of treatment with respect to ease of use, side effects, and recommendation to others (as measured using a 5-point Likert scale).

The provider will complete the assessment immediately following the procedure. The provider assessment elicits estimated blood loss, complications, ease of cervical dilation (with responses rated on an 11-point visual analog scale), procedure difficulty, recommendation for same patient and recommendation for other patients (as measured using a 5-point Likert scale).

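### Side effects are a named secondary outcome, but the only measure described is a 5-point acceptability rating, which does not give symptom occurrence by arm

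*Combined protocol and SAP*

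**What the plan says.** Five places in the combined protocol and SAP bear on this.

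- **Section 1 (Abstract)** lists among the patient-reported secondary outcomes "side effects, acceptability, and recommendation to friends (as measured on a 5-point Likert scale". Side effects stand apart from acceptability, but the only scale attached is the Likert scale.
- **Section 2 (Specific Aims)** does not list side effects. The patient and provider items there are "blood loss, pain, complications, provider assessment of difficulty, and provider and patient acceptance and recommendation for other patients".
- **Section 4 (Rationale)** states a symptom-specific difference between the routes: "Vaginal misoprostol is associated with fewer gastrointestinal side effects as compared to buccal administration". It gives no rates.
- **Section 5.5** says the patient survey is timed "to provide an accurate assessment of medication acceptability and side effects prior to anesthesia". The next sentence gives the content in two parts. One part is pain, on an 11-point VAS. The other part is "acceptability of treatment with respect to ease of use, side effects, and recommendation to others (as measured using a 5-point Likert scale".
- **Section 5.9** says "Both primary and secondary outcomes will be analyzed using t-tests or appropriate non-parametric comparison tests as appropriate", with non-parametric analysis for the VAS items. It does not mention a comparison of proportions.

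No section gives a symptom list, a yes/no item, a severity grade or an analysis of symptom occurrence.

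**The concern.** Whether a woman vomited and how acceptable she found the treatment with respect to side effects are different quantities. The first is occurrence and the second is tolerance. No mean or rank comparison of acceptability ratings can be turned into a proportion with symptoms or a risk difference. If the survey holds only what section 5.5 describes, the trial will report a named secondary outcome in a form that does not address the route difference cited in section 4.

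The design is well suited to recording occurrence. Under section 5, every woman takes both a buccal and a vaginal preparation, one active and one placebo, blinded, and both arms receive the same mifepristone. A difference in reported symptoms can therefore be attributed to the active route. The survey already falls after dosing and before anesthesia. Section 9 says data collection is complete on the day of the procedure, so symptoms not asked about then are not recovered later.

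**Working it through.** **Step 1. The plan's own figure.** The documents give no sample size or event rate for side effects. The only stated calculation, in section 5.10, is for procedure time: "with a two-tailed alpha of 0.05 and power of 90%, 33 women will be needed in each arm". With a difference of 4 minutes and SD 5:

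n per arm = 2 × [5 × (1.960 + 1.282) / 4]² = 2 × 4.052² = 32.8, so 33.

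The figure reproduces. It says nothing about side effects, but it fixes the number available for any comparison of them.

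**Step 2. What the text would yield.** Set side by side:

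| Place | Role of side effects | Measure attached |
|---|---|---|
| Abstract | secondary outcome, separate from acceptability | 5-point Likert, if the bracket covers it |
| Specific Aims | not listed | none |
| Section 4 | gastrointestinal effects differ by route | none |
| Section 5.5, purpose of survey | named alongside acceptability | none |
| Section 5.5, content of survey | an aspect of acceptability | 5-point Likert |
| Section 5.9 | covered only by the general sentence on outcomes | t-test or non-parametric test |

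No row supplies symptom occurrence by arm.

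**Step 3. What yes/no recording would give at 33 per arm.** All rates below are assumptions, chosen to span a range. For two-sided 0.05, power is the total binomial probability of all outcome pairs that reject, using (a) the z-test with pooled variance and (b) Fisher's exact test. The half-width of the 95% CI for the risk difference is 1.96 × √{[p1(1−p1) + p2(1−p2)] / 33}.

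| Assumed rates | Power, Fisher | Power, z-test | 95% CI half-width |
|---|---|---|---|
| 20% v 10% | 12% | 21% | ±17 points |
| 40% v 20% | 32% | 44% | ±22 points |
| 45% v 20% | 49% | 60% | ±22 points |
| 50% v 20% | 66% | 75% | ±22 points |

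Example for 50% v 20%: √[(0.25 + 0.16)/33] = 0.1115, and 1.96 × 0.1115 = 0.218. The closed-form approximation to z-test power agrees with the table. The pooled standard error is √(2 × 0.35 × 0.65/33) = 0.1174, and Φ[(0.30 − 1.96 × 0.1174)/0.1115] = Φ(0.63), about 73%.

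By the same approximation, 80% power would need 39 per arm for 50% v 20% and 82 per arm for 40% v 20%. Only differences of about 30 points would be detected with fair power.

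**The case against.** The strongest reply is that the text is loosely punctuated and the form is not shown. In the abstract, the bracket naming an 11-point VAS follows blood loss, complications and ease of dilation, and plainly does not put blood loss on a VAS. The Likert bracket after side effects, acceptability and recommendation need not govern all three either. Section 5.5 also gives side effects and acceptability as two things the survey is meant to assess. The form could carry symptom tick boxes. This stands, and it limits the point: a reader might infer that the trial cannot show a difference in gastrointestinal effects by route, but the documents support only that none is provided for.

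A reader might also infer that opposite effects of the two routes would cancel in one score. The documents do not support that:

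- Nothing says that ease of use, side effects and recommendation are pooled. They read naturally as separate items.
- No section names a side effect that is worse by the vaginal route. The only factor favouring the buccal route is in section 3, "it is known that patients prefer buccal administration". That is a preference, and it would offset a tolerability difference only if the items were combined.
- Cramping, the obvious candidate for an opposing symptom, is at least partly covered by the separate pain scale.

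Cancellation can be produced in a simulation by assuming equal and opposite effects on a single item, but it then follows from the assumption.

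Third, the trial is not designed to test tolerability. The hypothesis concerns dilation, the primary outcome is procedure time, and the gastrointestinal remark is part of one sentence of background. This also stands. It keeps the matter to a secondary outcome and makes a descriptive analysis the right one. It does not remove the need to say how an outcome named in the abstract is measured and analysed.

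**Conclusion.** The point holds as a gap in specification. Side effects are a named secondary outcome, and the rationale cites a gastrointestinal difference by route. The only measure described is an acceptability rating, and no analysis of symptom occurrence is given. Followed as written, the plan would yield tolerance ratings without the proportion of women with symptoms in each arm.

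It is a cheap improvement to one secondary outcome. The primary outcome, its analysis and the 33 per arm are unaffected. The gain is an estimate by route with an interval, not a confirmatory test: under the assumed rates the interval is about ±17 to ±22 points and power is between about 12% and 75%, depending on rates and test. These figures rest on assumed rates, 33 evaluable women per arm and two-sided 0.05. If the survey form already holds symptom items, what remains is to state them and their analysis in the protocol.

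**What to change.** - **Section 5.5:** add yes/no items for individual symptoms, at least nausea, vomiting and diarrhoea, to the existing pre-procedure survey. State that the Likert items are acceptability ratings, each analysed separately.
- **Section 5.9:** add one line: any gastrointestinal symptom (nausea, vomiting or diarrhoea) will be reported by arm as a risk difference with 95% CI, labelled descriptive, with the individual symptoms tabulated by arm.
- **Sections 1 and 2:** make the two outcome lists agree on side effects, and make clear in the abstract that the term means occurrence.

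The cost is under a minute of extra survey time per woman and one line of analysis text. Treatment, visits and sample size do not change. The items must be in place before women are surveyed, because data collection closes on the procedure day.

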### 9. Timeline

Recruitment will begin July 2015 and extend for approximately 9-months or once enrollment is complete. As recruitment will occur on patient's initial consultation for procedure and allocation and assessment will occur on the day of procedure, data collection will be complete the day of the patient's procedure. Data analysis will follow and will complete prior to the writing of the final report-please see timeline attached.

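### Complications are a secondary outcome with no time window, but their only described source is a provider form completed immediately after the D&E, and data collection closes that day, so complications after discharge cannot be counted

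*Combined protocol and SAP*

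**What the plan says.** Section 2 (Specific Aims) names among the secondary outcomes "total dilation required, blood loss, pain, complications, provider assessment of difficulty". The Abstract lists "provider estimation of blood loss, complications, ease of dilation". Neither defines a complication or says over what period it counts.

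Section 5.5 describes two instruments. For the first, "The patient will complete the survey immediately prior to the procedure". For the second, "The provider will complete the assessment immediately following the procedure", and its content is given as follows: "The provider assessment elicits estimated blood loss, complications, ease of cervical dilation", with difficulty and recommendation items after that.

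Section 9 (Timeline) states that "data collection will be complete the day of the" procedure.

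Section 5.9 (Data analysis) adds no definition or window: "Both primary and secondary outcomes will be analyzed using t-tests or appropriate non-parametric comparison tests as appropriate". It refers back to section 5.4 for how outcomes are recorded, but section 5.4 covers enrolment, mifepristone and the dispensing of envelopes, and collects no postoperative events.

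**The concern.** The label is wider than what is collected. A reader of the results will take complications to mean complications of the procedure under each regimen. The data will hold what the provider knew when filling in the form. A woman whose procedure was uneventful, and who later returns with bleeding, retained tissue or infection, would be counted as free of complications. A recorded zero could not be told apart from an event that came after the form.

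This is more than a missing detail, because section 9 states positively that collection ends that day. Ordinary clinical care may well pick up later events, but nothing in the plan brings them into the trial data. Section 7 hopes that the regimen could widen medication-only options, and section 5.11 expects the results to generalise widely, so the complication counts are likely to be read alongside the main result.

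**Working it through.** **Reading the sections together**

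| Period | Instrument described | Source |
|---|---|---|
| Before the procedure | Patient survey (pain, side effects, acceptability) | 5.5 |
| Up to just after the procedure | Provider form (complications, estimated blood loss, ease of dilation, difficulty) | 5.5 |
| Recovery, same day | None described; not excluded by the closing date | 5.5, 9 |
| After the day of the procedure | None; collection is already complete | 9 |

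The patient survey comes before the procedure, so it cannot record a postoperative event. That leaves one provider form for complications. No recovery-room form, discharge check, follow-up contact, later chart review or reporting of adverse events after the procedure appears in the visible text.

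**The plan's own calculation**

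Section 5.10 powers the primary outcome only, and "we chose 4-minute difference as clinically significant". With SD 5, two-sided alpha 0.05 and 90% power, the normal approximation is n per arm = 2 × (1.960 + 1.282)² × 5² / 4² = 32.8, rounded up to 33. The stated figure reproduces. It does not involve complications, so this point leaves it untouched.

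**Scale, on assumptions only**

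The documents give no complication risk (p) and no share arising after the form (f). Both are assumed below. With N = 72:

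- expected events = 72p
- expected unrecorded events = 72pf
- chance that at least one is unrecorded = 1 − (1 − pf)^72

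| Assumed p | Expected events | Unrecorded, f = 10% to 50% | Chance of at least one unrecorded |
|---|---|---|---|
| 2% | 1.4 | 0.1 to 0.7 | 13% to 52% |
| 5% | 3.6 | 0.4 to 1.8 | 30% to 84% |
| 10% | 7.2 | 0.7 to 3.6 | 52% to 98% |

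For example, at p = 5% and f = 50%: 72 × 0.05 × 0.5 = 1.8, and 1 − (1 − 0.025)^72 = 0.84.

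Even with perfect capture, zero events among 36 women in one arm gives an exact two-sided 95% upper limit of 1 − 0.025^(1/36) = 9.7%. That limit reflects the arm size and is not caused by the short window. The short window adds a different restriction: any such limit describes only the period up to the form.

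**The case against.** A fair defence has several parts, and most of them narrow the point.

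- **Recovery events.** A reader might infer that a woman who bleeds in recovery must be recorded as having no complication. The documents do not support that. The form is completed just after the procedure, not at the instant the last instrument leaves, and section 9 closes collection on that day, so a same-day event could be added. What stands is that no form or instruction provides for it.
- **Blood loss.** It is tempting to extend the criticism to this outcome. The Abstract and section 5.5 present it as a provider's estimate, which naturally means loss at the procedure. No defect is shown there.
- **Bias between arms.** Both arms are blinded and share the same window. A reader might infer a distorted comparison, but nothing in the documents points to one.
- **Large upper bounds.** Dividing the 9.7% limit by an assumed capture share gives alarming figures, such as 9.7% / 0.25 = 39%. The share is invented, and the 9.7% comes from having 36 women per arm. Such figures are not evidence of loss.
- **Promised conclusions.** No section plans a statement that the regimen is safe or that the routes have equal complication rates. The hypothesis concerns dilation and the primary outcome is procedure time. This limits the consequence but leaves the outcome undefined.
- **Hidden text.** The numbering runs from 5.7 to 5.9, and some pages, including any consent form, were not available. A collection step described there would not be visible. The same-day closure in section 9 does not depend on those pages.

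The defence does not answer the position after discharge: the outcome is named without limit, and the plan stops looking that day.

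**Conclusion.** The point holds in a limited form. Complications after discharge cannot enter the data as the plan is written, and events in recovery have no described route into it. The result is under-ascertainment of one secondary safety outcome in both arms. Procedure time, the 33 per arm and the blood-loss estimate are not affected.

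The size is unknown. The table above shows only what would follow if the risk were 2% to 10% and if 10% to 50% of events came after the form; neither range comes from the documents. The conclusion itself rests on sections 1, 2, 5.5 and 9 read together and needs no rate. The plan should be changed in its collection or, failing that, in its label.

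**What to change.** **Preferred.** In section 5.5, keep the provider form and add complications up to discharge from recovery, taken from the existing chart. In section 9, replace same-day closure with one chart check on a fixed day, stated in advance, for unplanned visits, repeat evacuation, transfusion and treatment for infection. The existing coordinator would do it identically in both arms while blinded. Section 8.1 gives the coordinator a part in treatment allocation and concealment, so the text should say that the check is made without access to the allocation list. State the resulting window wherever the outcome is named.

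**Cost.** A little more abstraction work for each of 72 women. Care received elsewhere will be missed, and the report should say so. A telephone call might find some of it, but would add contact and confidentiality steps, so it is not needed for this fix. The sponsor should confirm that the consent form covers the later chart check.

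**If same-day closure is kept.** In sections 1 and 2, label the outcome *provider-reported complications up to completion of the immediate post-procedure form*, and limit conclusions to that window. This costs only wording. The shorter label *intraoperative complications* fits less well, because the form asks about complications in general and an expulsion before the procedure, a concern raised in section 3, would fall outside it.
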